1 BACKGROUND/SCIENTIFIC RATIONALE

Gastroparesis is a disorder characterized by impaired gastric emptying in the absence of obstruction of the proximal gastrointestinal (GI) tract. Symptoms typically include postprandial fullness, nausea, vomiting, bloating, and pain. In severe cases, anorexia and weight loss may be present. It is estimated to affect up to 5 million persons in the US with an age-adjusted prevalence of 37.8 per 100,000 persons [1]. The most common identifiable etiology is diabetes mellitus in 30% but 36% are classified as idiopathic [2]. Gastroparesis is a chronic disabling condition that is associated with a significantly worse outcome compared to age and sex matched controls [3].

Currently, the only FDA approved medication for treatment of gastroparesis is metoclopramide. Recently, metoclopramide was issued a black box warning by the FDA because of the risk of adverse events, especially tardive dyskinesia, a potentially irreversible neurologic condition characterized by uncontrollable facial, oral, and lingual movements. National guidelines suggest the risk of developing tardive dyskinea is 1-15% [4, 5]. Although the actual risk of TD may be much lower, the evidence supporting the use of metoclopramide in gastroparesis is fairly weak, it may not alleviate symptoms of anorexia and weight loss, and development of other agents with better efficacy and less adverse effects is needed [6].

Macrolide antibiotics have also been used in the treatment of gastroparesis. They act on motilin receptors to cause pro-motility effects but have no central effects on nausea, hunger, and appetite stimulation [7, 8]. In addition, tachyphylaxis may limit long-term use.

Olanzapine is a second generation anti-psychotic that is FDA approved for the treatment of schizophrenia and bipolar disorder. Second generation anti-psychotics typically have fewer extrapyramidal side effects (e.g. akathisia, dystonia, parkinsonian symptoms) as well as tardive dyskinesia compared to older anti-psychotics [9, 10]. However, they do carry potential for serious metabolic risk, specifically weight gain, hypertension, hyperlipidemia, and ultimately development of diabetes mellitus. Olanzapine has been associated with one of the highest risks of weight gain among atypical anti-psychotics [11, 12]. It is unclear if this is related to other actions or if it is related to attenuation of the disease process. Patients with schizophrenia may have a predisposition towards obesity with a prevalence of up to twice the general population [13]. Genetic predisposition, higher prevalence of smoking, and neuroendocrine changes associated with psychosis have all been postulated as possible contributing factors to increased obesity in schizophrenia and bipolar disorder [14-18].

Olanzapine may also have other therapeutic effects outside of controlling psychosis. Phase I and II studies have shown olanzapine significantly relieves nausea and emesis in a palliative care setting [19-21]. It was found to be safe in both trials and helped stimulate appetite and augment weight gain. There is also evidence that olanzapine may be beneficial in the

treatment of eating disorders. Several double blind, placebo-controlled trials have shown benefit of olanzapine in terms of attaining goal BMI and improving psychological measures [22-24]. Furthermore, the medication was well tolerated in this population without development of adverse metabolic events [22, 23, 25].

Olanzapine has actions at multiple receptors throughout the body, which may make it a unique drug for the treatment of gastroparesis. These include antagonism of dopamine, serotonin, $alpha_1$ adrenergic, muscarinic, and histamine receptors [26, 27]. Many of these receptors, especially D₂ and 5HT₃, are involved in the signaling of nausea and emesis [28]. As a result, olanzapine may have anti-nausea properties that could be utilized in gastroparesis. Antagonism of D₂ receptors may also provide motor effects in the stomach, as this is one of the main mechanisms of action for metoclopramide [29-31].

Furthermore, olanzapine may also have effects on gut neurohumoral signaling that are important in regulation of appetite and weight. Long-term use of olanzapine between 26 and 52 weeks has been shown to increase plasma levels of ghrelin in mouse models as well as humans on long-term treatment for schizophrenia [32-34]. However, short-term use between 2 to 9 weeks may actually decrease levels of ghrelin [35-37]. Ghrelin is a hormone that is produced by the gut, stimulates appetite, and has been shown to improve symptoms as well as promote gut motility in gastroparesis [38-40]. Previous data have shown that olanzapine may affect only ghrelin levels whereas other gut hormones, e.g. peptide YY, pancreatic polypeptide, leptin and GLP-1 were not affected [34, 37]. Because of this data as well as limited resources, only ghrelin is going to be evaluated during this study.

There are few options currently that are efficacious and safe for the treatment of gastroparesis and development of other therapeutic options is needed. Furthermore, in patients with severe gastroparesis causing anorexia and weight loss, polypharmacy is often needed to stimulate appetite and alleviate symptoms. Olanzapine may possess unique properties, which makes it a potentially attractive therapeutic option for gastroparesis. We hypothesize that olanzapine will be effective and safe in controlling symptoms as well as stimulate appetite in gastroparesis. We also hypothesize that olanzapine will promote gastric motility. Finally, we hypothesize that olanzapine will stimulate the secretion of ghrelin, thereby aiding in the treatment of gastroparesis. This pilot study may provide further insight into the efficacy and safety of olanzapine in gastroparesis, which could be utilized in a larger randomized, placebo-controlled prospective study in the future.

2 OBJECTIVES

Aim 1: Investigate the efficacy and safety of olanzapine in the treatment of nondiabetic gastroparesis.

We will utilize the gastroparesis cardinal symptom index daily diary (GCSI-DD) and an appetite visual analog scale (VAS) to compare severity of symptoms before and after treatment with olanzapine. Subjects will undergo regular testing of blood glucose, insulin, hemoglobin (Hgb) A1c, body mass index (BMI), liver enzymes, thyroid stimulating hormone (TSH), and prolactin levels during the study as well as after treatment completion to determine the safety of the medication. All adverse events will be compiled to investigate the tolerability of the medication.

Aim 2: Determine whether olanzapine has prokinetic effects on gastric emptying in gastroparesis.

We aim to test gastric motility, including gastric emptying and antroduodenal contractility parameters, by wireless motility capsule (WMC) before and at the completion of the study to determine if olanzapine has any pro-motility effects in gastroparesis.

Aim 3: Examine the effects of olanzapine on neurohumoral regulation of eating and appetite.

We seek to determine whether olanzapine promotes secretion of ghrelin in gastroparesis.

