6 STUDY DESIGN AND PROCEDURES

This is a pilot study of 10 consecutive subjects ages 18 – 80 with documented delayed gastric emptying within the past 2 years and history of nausea, vomiting, bloating, anorexia, early satiation, post-prandial fullness, and weight loss for at least 6 months without structural or organic cause will be enrolled. This will be an open label trial without a placebo arm to determine efficacy and safety of the medication in this population. This will be a single center study with subjects being enrolled at the University of Michigan. [name] at Massachusetts General Hospital will act as a co-I and will assist with data analysis but will not enroll any patients. [name] will receive only de-identified information.

The study will consist of a screening/baseline period of up to 30 days, an 8-week treatment period, and a 14-day post treatment safety follow-up visit and assessment of symptoms.

Screening/Baseline:

Subjects will participate in a screening/baseline visit within 30 days prior to study dosing. Subjects will be instructed to fast prior to the screening visit at which time they will undergo blood sampling for complete blood count (CBC), complete metabolic panel (CMP), lipid profile, insulin, Hgb A1c, prolactin, TSH, and urine or blood pregnancy screen (if applicable). A baseline ECG will also be performed. Ghrelin levels will be measured. Baseline vital signs, height, weight, and BMI will also be calculated. They will also have their gastric emptying assessed by wireless motility capsule (WMC). To be eligible for the study, the subjects' gastric emptying time, as determined by WMC, needs to be greater than 5 hours. Potential subjects will complete the gastroparesis cardinal symptom index daily diary (GCSI-DD) evaluation, appetite visual analog score (VAS), and Bristol Stool Form Scale (BSFS) for a minimum of 7 days to determine baseline level of symptoms [41]. Questionnaires will be completed in the evening after dinner. Mean total GCSI-DD score must be ≥ 2 in order to qualify for the study.

Week 1 – Week 8:

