Subjects will initially start on olanzapine 2.5 mg by mouth daily to be taken at bedtime. Subjects will return on days 7 and 14 to determine response to medication. Medication dose can be increased to 5 mg on day 7 and 10 mg on day 14, respectively, based on incomplete symptom response, which is defined as a mean change in GCSI-DD score < 0.5 from baseline. Height and weight will be measured on Day 7. The total dose of olanzapine will not exceed 10 mg daily during this study. Subjects will be monitored for adverse events and undergo blood sampling for glucose, insulin, and Hgb A1c on day 14. Vital signs, height, weight, and BMI will also be evaluated. Subjects will be instructed to bring their study medication with them on day 14 for assessment of study drug accountability.

Subjects will be contacted by phone at least once within 2 weeks following the day 14 visit to assess for potential side effects. Subjects may also come in for an extra/optional study visit between the Day 14 and Day 35 visits, if warranted by side effects.

Subjects will return on day 35 to monitor for adverse events, vital signs, height, weight, BMI, and glucose check.

During the study, subjects will rate their gastroparesis symptoms on a daily basis by completing the GCSI-DD and appetite VAS questionnaires. Subjects will also record daily the number of stools and their consistency [42]. Subjects will be asked to complete all diaries after the evening meal. The subjects will fast prior to returning to clinic on the morning of day 56 to undergo assessment of their gastric emptying time by WMC and complete an appetite VAS. Blood sampling for LFTs, glucose, insulin, Hgb A1c, and ghrelin levels will be performed. Vital signs, height, weight, and BMI will also be measured. All remaining study medication will be returned to the clinical unit for final drug accountability. Subjects will continue to rate their gastroparesis symptoms for 14 days following the end of dosing.

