Post-Treatment Assessment:

At the conclusion of 56 days of dosing, subjects will return for a follow-up visit 14 days (+ 2 days) after the last dose of study medication. All subjects will have blood sampling for CBC, CMP, lipid profile, TSH, prolactin, insulin, Hgb A1c, and ghrelin. Height, weight, and BMI will be calculated. One final appetite VAS will be completed. The duration of each patient's participation in the study from screening to follow-up visit will be approximately 14 weeks.

Subjects are free to discontinue participation in the study at any point. If a subject decides to prematurely discontinue from the study, they will be contacted within two weeks for safety follow-up visit(s). Reasons for withdrawal will be documented by the PI. If the reason for removal of a subject from the study is an AE, the principal specific event will be recorded on the CRF. The subject will be followed until the AE is resolved.

Gastric Motility:

Gastric motility will be tested by using the WMC wireless capsule system (The SmartPill Corporation, Buffalo, NY). This offers a potentially more complete examination into possible etiologies for gastroparesis including delayed gastric emptying as well as gastric and small bowel contractility abnormalities. We will follow the protocol for measuring gastric emptying by wireless motility capsule as described previously in the literature [43]. Gastric emptying time (GET) is defined as the duration of time from capsule ingestion to entry of the capsule into the duodenum. Subjects will swallow the WMC capsule with 50 ml of water followed by ingestion of a standardized meal comprising of a nutrient bar, which has a total caloric value of 255 kcal (72%)

carbohydrate, 24% protein, 2% fat, and 2% fiber) [44]. Because of the low risk of capsule retention especially once the capsule enters the colon, plain abdominal radiograph (KUB) will be performed only if there is no documentation of the capsule passing the ileocecal valve and the patient has symptoms of capsule retention. Pressure data recorded by the WMC capsule will be analyzed for 1 hour before and after the WMC empties the stomach (GET). The analyzed parameters are: number of contractions (Ct), and motility index defined as: MI = Ln (sum of pressure amplitudes * number of contractions +1) [45].

Stopping Criteria:

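### TSH and prolactin, two of the safety measures named in Aim 1, are never scheduled while subjects are taking olanzapine

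*Combined protocol and SAP*

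**What the plan says.** Aim 1 in Section 2 lists glucose, insulin, HbA1c, BMI, liver enzymes, TSH and prolactin for regular testing. It places that testing both in the study and after it, ending with "liver enzymes, thyroid stimulating hormone (TSH), and prolactin levels during the study as well as after treatment completion", and gives the purpose as judging the drug's safety.

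Section 6 then names the tests visit by visit:

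- Screening, within 30 days before dosing: "blood sampling for complete blood count (CBC), complete metabolic panel (CMP), lipid profile, insulin, Hgb A1c, prolactin, TSH". Also "Ghrelin levels will be measured".
- Day 7: height and weight.
- Day 14: subjects "undergo blood sampling for glucose, insulin, and Hgb A1c on day 14".
- Day 35: "Subjects will return on day 35 to monitor for adverse events, vital signs, height, weight, BMI, and glucose check".
- Day 56, fasting, in the morning: "Blood sampling for LFTs, glucose, insulin, Hgb A1c, and ghrelin levels will be performed".
- Post-treatment: "subjects will return for a follow-up visit 14 days (+ 2 days) after the last dose of study medication", when "All subjects will have blood sampling for CBC, CMP, lipid profile, TSH, prolactin, insulin, Hgb A1c, and ghrelin".

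The phone contact after Day 14 and the optional extra visit list no laboratory tests. Section 10 gives a general rule: changes from baseline are tested at the post-treatment assessment, and a hierarchical regression uses all measurement times. It does not name TSH or prolactin.

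**The concern.** For TSH and prolactin, the aim and the schedule do not match. A test of whether the drug moves an analyte needs at least one value taken while the drug is being given, and these two have none. If the plan is followed exactly, the safety conclusion on both rests on one value before treatment and one about two weeks after it.

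Three features of the protocol make this more than loose wording. Section 8 makes safety part of the primary outcome. Section 6 lists raised prolactin among the common potential adverse effects. Section 3 offers withdrawal if thyroid dysfunction arises during the study, but no on-drug thyroid test is scheduled that could reveal it.

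The practical danger is a misread null. An unchanged TSH or prolactin at follow-up could be reported, and carried into the larger trial that Section 1 has in mind, as showing no effect on treatment when nothing was measured on treatment.

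**Working it through.** **Step 1. Scheduled values per subject.** Inputs: the Section 6 visit text for Screening/Baseline, Week 1 to Week 8 and Post-Treatment Assessment. Glucose and liver enzymes are counted under the metabolic panel at screening and follow-up.

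| Measure | Screening | Day 14 | Day 35 | Day 56 | Follow-up | On-drug values |
|---|---|---|---|---|---|---|
| Glucose | yes | yes | yes | yes | yes | 3 |
| BMI | yes | yes | yes | yes | yes | 3 (height and weight also on Day 7) |
| Insulin | yes | yes | no | yes | yes | 2 |
| HbA1c | yes | yes | no | yes | yes | 2 |
| Liver enzymes | yes | no | no | yes | yes | 1 |
| TSH | yes | no | no | no | yes | 0 |
| Prolactin | yes | no | no | no | yes | 0 |
| Ghrelin (Aim 3, for comparison) | yes | no | no | yes | yes | 1 |

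So 2 of the 7 Aim 1 measures have no on-drug value.

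**Step 2. Totals over the trial, if all 10 subjects complete.**

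- As written: 2 analytes × 2 draws × 10 subjects = 40 values, of which 0 are on drug.
- With both added on Day 56: 2 × 3 × 10 = 60 values, of which 2 × 1 × 10 = 20 are on drug.

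**Step 3. Distance between the two existing draws.**

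- Longest: 30 days of screening + 56 days of dosing + 16 days = 102 days.
- Shortest: 0 + 56 + 14 = 70 days as an arithmetic floor. Eligibility needs at least 7 diary days, so if the diary starts at the screening visit the shortest gap is 7 + 56 + 14 = 77 days.

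On either count, the whole dosing period falls between the draws. The later draw comes at about study day 56 + 14 = 70 to 56 + 16 = 72.

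**Step 4. What the planned analysis would use.** Under Section 10's general rule, the paired change for these analytes is follow-up minus screening. The regression over all measurement times has the same two points. Section 8's multiple imputation cannot fill the gap, because no on-drug TSH or prolactin is observed in any subject.

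**Step 5. What the fix could show.** If none of 10 subjects had an abnormal Day 56 value, the exact two-sided 95% upper limit for the true proportion would be 1 − 0.025^(1/10) = 30.8%. That is descriptive pilot information and does not demonstrate safety. Because Section 4 requires normal TSH and prolactin at entry, any abnormal Day 56 value would be new since screening.

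**The case against.** The best defence is that Section 6 counts the screening period as part of the study. A screening draw is then in the study, a follow-up draw is after treatment, and Aim 1 is met to the letter. Regular testing is also said of all seven measures together, with no frequency set for each. This reading is possible, but it leaves both analytes without an on-drug value, and one pre-dose draw is a poor fit with regular testing of a drug's safety.

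Second, Section 10 names neither analyte, and the comparison it describes can be run as written, since both are drawn at the post-treatment visit. That is correct. The limit is on what the comparison can mean, not on whether it can be computed.

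Third, the risk is partly covered. Section 3 calls the prolactin effect minimal in schizophrenia and the thyroid risk small. Symptoms of hyperprolactinemia have their own withdrawal option, side effects can prompt an extra visit, and the stated purpose in Section 6 concerns severe complications. All of this stands and narrows the loss to asymptomatic, quickly reversible changes. It does not explain why Aim 1 names the two analytes as safety evidence.

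Fourth, lipids are also drawn only at screening and follow-up, although Section 6 lists hyperlipidemia in the same sentence as raised prolactin. The clinical argument applies to lipids too. They are not among the Aim 1 measures, so the mismatch with Aim 1 does not.

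Last, Figure 1, the subject timeline, is not shown in the text available for review and might carry a laboratory schedule. The written lists are explicit, so a different schedule there is unlikely. If it did differ, the two would need reconciling.

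**Conclusion.** The concern holds. On the written schedule, TSH and prolactin have no on-drug value, while the other five Aim 1 measures have one to three. Any statement about the drug's effect on these two analytes would rest on 40 off-drug values.

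The consequence is limited. A persistent change would appear at follow-up, and symptomatic hyperprolactinemia has its own trigger. What is lost is an asymptomatic change that resolves within 14 to 16 days of stopping. How often that would happen is unknown, because the documents give no reversal rate for either analyte.

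The conclusion assumes that the visit text is the full schedule and that Section 10's rule on changes from baseline covers the Aim 1 laboratory measures. It should be corrected because the remedy is cheap, not because the trial's main result depends on it.

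**What to change.** Add TSH and prolactin to the fasting Day 56 morning draw. Report the change from screening to Day 56 as the descriptive on-drug safety comparison, and keep the follow-up draw to show whether any change persists. This is the three-point schedule already used for ghrelin.

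The cost is 2 × 10 = 20 assays on blood already being taken, with no new visit or needle stick. An unexpected abnormal result may need clinical follow-up.

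Day 56 is the end of dosing, so this does not protect subjects during treatment. If the thyroid withdrawal option in Section 3 is meant to rest on a laboratory value, add one TSH at Day 14 or Day 35. That is 10 more assays, 30 in all. Day 14 is the surer choice, because the text does not say whether the Day 35 glucose check is a venous sample.

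If no assays are added, state in Aim 1 and in the safety conclusion that TSH and prolactin were assessed only off drug.

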3 EXPECTED RISKS/BENEFITS

The data accumulated in this study will advance our understanding of the pathophysiology of gastroparesis, and may provide important information on whether olanzapine is helpful in the treatment of idiopathic gastroparesis.

There are potential direct benefits for all gastroparesis subjects in this study. On study entry, physiologic tests of gut function and motility will be performed that may provide new insight into causes of symptoms in patients with IBS. In addition, all subjects will be seen by the PI and/or study team frequently during the study. Adverse events, vital signs, and laboratory parameters will be assessed to monitor overall safety and tolerability of the medication. Survey information will also be obtained using validated questionnaires including GCSI-DD, appetite VAS, and BSFS. The GCSI-DD is a validated questionnaire composed of twelve questions that takes approximately 10 minutes to complete. The appetite VAS is a single item questionnaire that tracks changes in appetite over time. This will take approximately 1 minute to complete. The BSFS is a questionnaire that allows researchers and subjects track changes in bowel form and frequency. This will take approximately 1 minute to complete. This frequent and comprehensive assessment provided as part of participating in this study may allow for closer monitoring of disease course.

There are potential risks for subjects, including:

1. Olanzapine Risks:

Weight gain: Weight gain is a known risk when patients with schizophrenia or other psychiatric illnesses are taking olanzapine. This may also predispose the patient to develop underlying obesity, hyperlipidemia, diabetes mellitus, and coronary artery disease. However, this may be a risk inherent to this specific population and may not be applicable to the general population. Human studies in patients with anorexia nervosa and other eating disorders have shown the safety and tolerability of olanzapine. We will exclude anyone with a history of diabetes mellitus or hyperglycemia. We will also monitor the subjects closely during the study period and anyone who exhibits hyperglycemia (fasting glucose > 150 mg/dl or non-fasting glucose > 180 mg/dl), and/or rapid weight gain (> or = 5 kgs/week) will be taken off the study drug. Subjects will continue to be monitored for 14 days after completion of the study drug.

Orthostatic hypotension: Subjects who are taking concomitant anti-hypertensive medications will be warned about the risk of potentiating orthostatic hypotension with olanzapine. They will be asked to exercise caution especially when changing positions suddenly.

Hyperglycemia: Subjects will be given a handout at the start of the trial discussing potential symptoms of hyperglycemia, including excessive thirst, frequent urination, blurry vision, and fatigue. Subjects will be asked to notify the study coordinator immediately if they have any of these symptoms.

Somnolence: Subjects will be asked to take the olanzapine at bedtime to minimize the effects.

Constipation: Subjects will be instructed on potential effects of olanzapine on bowel habits and may take laxatives to help with constipation.

Olanzapine appears to be well tolerated in placebo-controlled trials. The only adverse events occurring more frequently with olanzapine compared with placebo were somnolence, constipation, and weight gain. However, other adverse events have been reported in the literature and will be listed below.

Extrapyramidal side-effects: Animal models as well as human studies have shown low potential for olanzapine to cause extrapyramidal side-effects (EPS), such as parkinsonism, akathisia, and dystonia. Subjects will be monitored during the study period for development of EPS.

Thyroid dysfunction: There is a small risk for causing thyroid dysfunction. Thyroid levels will be checked as part of the screening period and patients with underlying dysfunction will be excluded from the study. If thyroid dysfunction occurs during the study, they will have the option of withdrawing from the study.

Hyperprolactinemia: Olanzapine produces minimal effects on prolactin levels in patients with schizophrenia. This will also be monitored prior to starting the study drug and subjects with abnormal levels of prolactin will be excluded. Patients who exhibit signs and symptoms of hyperprolactinemia during the study period will be given the option of withdrawing from the study.

Seizures: Lowering of the seizure threshold has been seen in subjects taking olanzapine. This may be a dose-dependent response and certain factors including younger age, female sex, and concomitant SSRI use causes higher serum levels of olanzapine. We intend to use a small dose of olanzapine and will exclude subjects with a history of seizure disorder.

